7.2 Sample size and justification

407 participants will be recruited for the study.

This calculation is based upon recommendations by Riley et al²⁸ using the recommended margin of error of ≤ 0.05 , for a binary outcome that occurs in half of individuals attending the vulval clinic with up to nine predictors in the final dataset. A sample size of 370 people (185 people with the outcome LS and 185 non-LS) is needed to target a confidence interval of 0.45-0.55 for the overall outcome proportion of 0.5 and to target a mean absolute error of 0.062 between observed and true outcome probabilities. The final recruitment figure of 407 participants includes a 10% increase for missing data.

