Sample size estimate	
A sample size of 370 people (185 people with the outcome LS and 185 non-LS) is needed to target a confidence interval of 0.45-0.55 for the overall outcome proportion of 0.5 and to target a mean absolute error of 0.062 between observed and true outcome probabilities based on up to nine predictor variables.
 
The final recruitment figure of 407 participants includes a 10% increase for missing data

Number of participants	407 participants will be recruited to the study.
Eligibility criteria	
Inclusion criteria:
 
 • Adults (≥ 18 years of age) • Female • New presentation to a specialist clinic (secondary care or community hub) with a vulval skin complaint 
Exclusion criteria:
 
 • Inability to provide informed consent • Patients with surgical alteration of vulval skin as part of gender reaffirming surgery, or patients not born with a vulva • More than 2 weeks since initial consultation in specialist clinic

Description of interventions	
This is an observational study. There are 17 Delphi-agreed LS diagnostic criteria being tested in this study.
 
Patients will have one study visit lasting approximately 30 minutes. The study visit will include 2 clinical examinations for diagnostic assessment. At one centre (Nottingham), there will be a potential third assessment for testing of the inter-observer variability of the diagnostic criteria.
 
The reference standard diagnostic assessment will be undertaken by the patients' managing clinicians.
 
A trained blinded assessor will examine the patient to record the presence or absence of the Delphi-agreed diagnostic criteria.
 
Information will also be collected from the patient including, age, ethnicity, post code (for socioeconomic status), patient rating of the condition on the day of assessment, physician global assessment of severity, symptom duration, diagnosis of LS prior to clinic appointment, previous diagnosis of a vulval condition, treatments received, treatment duration, whether on active treatment at the time of recruitment, treatment length, and clinical assessment of 'early' or 'late' stage LS.
 
Clinical photographs will be taken in line with usual care and participants can opt out of these being used for research purposes if they wish.
 
Skin biopsy will be taken in line with usual care. Histological diagnosis will be recorded if patients have undergone a biopsy.

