3.3 Index and reference tests

3.3.1 Index test

The international electronic-Delphi exercise involving expert health professionals and patients (see section 1.3 for further detail) has identified a list of 17 diagnostic features which were agreed to be 'critical', or 'important but not critical' in the diagnosis of LS. The SHELLS diagnostic test accuracy study is using this list of 17 diagnostic features as the index test.

A diagnostic criteria assessment looking for the presence or absence of these 17 diagnostic features, using experience and clinical judgement, will be performed by an assessor blinded to the reference standard (specialist's diagnosis – see section 3.3.2).

List of diagnostic features to be assessed as part of the index test:

Critical:

- Changes in the anatomy of the genital area
- Response to topical corticosteroids
- Whiteness
- Itch
- Burying of the clitoral area

Important but not critical:

- Absence of vaginal involvement
- Fissuring
- Crinkly skin
- Bruising/bleeding under the skin
- Fissuring at the back entrance to the vagina
- Pain/soreness unrelated to sexual activity
- Pain/soreness related to sexual activity
- Skin thickening
- Loss of skin stretchiness

- Erosions
- Irritation
- Perianal fissure

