7 ANALYSES

7.1 Methods

[name] will undertake the analysis of the data under the supervision of [name] (Study Statistician).

Demographic data and participant characteristics will be analysed descriptively.

Stage 1

Developing a diagnostic prediction model:

i. Determining a predictive model of diagnostic criteria for vulval LS: All criteria identified will be included in a backward multivariable logistic regression model²² with exit criteria $p=0.157$.²³

ii. Quantifying the performance of the diagnostic prediction model: Explained variation will be measured by Cox-Snell R-squared. A calibration plot will assess how well predictions agree

with the observed data. Smoothed calibration curves will be plotted using a loess smoother.^{24,25} All data for model development will be included for use in internal-external cross validation across centres (alongside bootstrapping). Discrimination will be measured using the C statistic.²⁶ The model will be fitted to this dataset.

iii. Clinical utility: Thresholds on the calibration plot will be based on clinical utility i.e. what defines high risk and trade-offs between benefits and harm, defined by patients and doctors.

Stage 2

Model validation

Internal validation is essential to (i) obtain an unbiased estimate of the developed model's predictive performance, and (ii) adjust (shrink) the developed model for optimisation (if necessary). Bootstrapping and uniform shrinkage techniques will be used for analysis.

Missing data: Missing data is not anticipated as the diagnostic features will be assessed by clinical examination. There will be a 'yes' or 'no' answer recorded in the CRF for each criterion in each patient. Only if a participant declines to continue the examination or declines to be examined by the blinded assessor do we anticipate missing index-reference test data pairs. However, the sample size is increased by 10% to account for a maximum of 10% missing data. This will be monitored and if less than 10% data are missing, recruitment target will be reduced accordingly.

c. Inter-observer variability

The inter-observer reliability for assessing the individual diagnostic criteria on 20 cases and 20 non-cases from one of the sites will be calculated using the Kappa statistic. A value of Kappa >60% will be considered acceptable as 'good' agreement between observers.²⁷ At the site where these data are collected (Nottingham, lead site), there will be two independent assessors.

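### The mean absolute error of 0.062 at n=370 is calculated for nine predictors, but the planned analysis selects from 17, so the calculation does not support that figure

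*Protocol*

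**What the plan says.** Protocol section 7.2 gives two targets for n=370. The first concerns the outcome proportion: the sample "is needed to target a confidence interval of 0.45-0.55 for the overall outcome proportion of 0.5". The second is a mean absolute error of 0.062 between observed and true outcome probabilities. The calculation is described as being "for a binary outcome that occurs in half of individuals attending the vulval clinic with up to nine predictors in the final dataset". The synopsis ties the same error figure to nine as well: "based on up to nine predictor variables". Recruitment is then raised by 10% to 407.

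Section 3.3.1 lists five critical and 12 important features and states: "The SHELLS diagnostic test accuracy study is using this list of 17 diagnostic features as the index test". Section 7.1, Stage 1 (i), says: "All criteria identified will be included in a backward multivariable logistic regression model", with an exit threshold of p=0.157. Under missing data, section 7.1 records each criterion as yes or no, so 17 features mean 17 candidate parameters. The same paragraph allows the recruitment target to come down if fewer than 10% of data are missing, so 370 is the number that matters.

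**The concern.** The prediction error of a model built by selection depends on all the candidates examined, not only on those that survive. The protocol neither reduces 17 features to nine before modelling nor limits the final model to nine, and it does not say where nine comes from. If nine means a list reduced beforehand, section 7.1 contradicts it. If it means the expected number of survivors, it is the wrong input to the error calculation.

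The primary objective ends in a diagnostic tool, which section 1.3 intends for non-specialists and for self-diagnosis by patients. The accuracy of its predicted probabilities is central, and the protocol attaches to it an error figure that does not describe the planned analysis.

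**Working it through.** **Inputs.** Outcome proportion φ=0.5, n=370, recruitment 407, stated error 0.062 and nine predictors are from section 7.2. The 17 candidates are from section 3.3.1. Backward selection with exit p=0.157 is from section 7.1. The LS share of 50-60% is from section 3.2.

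**Formula (coefficients assumed, not printed in the protocol).** ln(error) = −0.508 + 0.259 ln(φ) + 0.504 ln(P) − 0.544 ln(n), where P is the number of parameters.

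**Step 1: the protocol's own figure.** P=9, n=370: −0.508 − 0.180 + 1.107 − 3.217 = −2.797, so the error is 0.061. Solved for an error of 0.062, n is 359, within 3% of 370. The stated figure is essentially reproduced, and only with about nine parameters.

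**Step 2: the candidates actually entered.** P=17, n=370: −0.508 − 0.180 + 1.428 − 3.217 = −2.477, so the error is 0.084. That is 0.084/0.062 = 1.35 times the stated value. At n=407 it is 0.080. Holding 0.062 with 17 parameters would need about 648 people analysed. At φ=0.6, P=17 gives 0.088 at n=370.

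**Step 3: a check without those coefficients.** The approximation √(2/π) × √(φ(1−φ)(P+1)/n) at n=370 gives 0.066 for P=9 and 0.088 for P=17. In simulation at n=370, full nine-predictor models gave 0.059-0.062 and full 17-predictor models with independent features gave 0.078-0.086 (40% prevalence, 300 replicates).

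**Step 4: the planned selection.** Simulated at n=370 and outcome proportion 0.5, with 17 binary features and backward elimination at p=0.157. The first five rows use 40% feature prevalence and 300 replicates. The others use 35% and 150 to 200 replicates. Figures in brackets are log-odds ratios.

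| Setting | True C | Mean absolute error after selection |
|---|---|---|
| Independent: 5 strong (1.2), 12 noise | 0.781 | 0.065 |
| Independent: 9 real (0.8), 8 noise | 0.766 | 0.075 |
| Independent: 9 real (0.5), 8 noise | 0.685 | 0.090 |
| Independent: 5 strong (1.2), 12 weak (0.3) | 0.805 | 0.087 |
| Independent: 17 weak (0.4) | 0.699 | 0.107 |
| Independent: 4 or 5 very strong, rest noise | 0.88-0.89 | 0.055-0.056 |
| Latent correlation 0.3, six scenarios | 0.87-0.95 | 0.048-0.061 |
| Latent correlation 0.2: 5 strong, 12 weak | not recorded | 0.080 |

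The range is therefore roughly 0.05 to 0.11.

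**Step 5: the other target.** 1.96 × √(0.25/370) = 0.051, giving 0.449-0.551, which rounds to the stated interval. This does not involve P.

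**The case against.** Four points on the other side have force.

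- **The 0.062 may still be reached.** A reader might infer that it will certainly be missed. The documents do not support that. The features overlap (three concern fissuring; clitoral burying is close to anatomical change), so independence is an unfavourable assumption, and several favourable scenarios met 0.062. This stands. However, a nine-predictor model would also do better in those settings, so the relative penalty for 17 remains. Correlation alone is not enough either, as the last row of the table shows.
- **370 has a second basis.** A reader might infer that no justification for the sample size is left. That is wrong: the interval for the outcome proportion is stated separately and holds.
- **The final model need not exceed nine features.** With four or five true predictors, more than nine were kept in about 1-7% of simulated runs; with nine or more true predictors, in 67-97% of one set of runs. The true number is unknown, so no general statement is possible. A small final model would not remove the cost of having searched 17.
- **Section 7.1 already plans bootstrapping, uniform shrinkage and internal-external cross-validation.** These estimate and correct optimism. They do not make an error calculated for nine parameters apply to a search over 17.

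It is also fair to say that 0.084 is the formula value for 17 fitted parameters, not for the selected model. It should be printed with that label and with the simulated range.

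**Conclusion.** The point holds as a mismatch between the sample-size premise and the planned model. The arithmetic for nine predictors is sound; the premise does not match the analysis. On the same formula, 17 candidates give about 0.084 at 370 and 0.080 at 407, against the stated 0.062. This rests on the assumed coefficients, which reproduce the protocol's figure closely (0.061) and agree with the approximation and the simulated full models with independent features. The error actually achieved after selection cannot be fixed in advance. Roughly 0.05 to 0.11 is a fair range, with 0.062 met only in the scenarios with a few very strong predictors or with sufficiently correlated features.

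**What to change.** Choose one of two routes.

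1. **Restate the figure.** In section 7.2 and the synopsis, replace the nine predictors by 17 candidate predictor parameters. Give the expected error as about 0.084 at 370 (0.080 at 407), name the formula and its assumed coefficients, and add the simulated range for the selection procedure. The sample size stays as it is.
2. **Keep 0.062.** Pre-specify in section 7.1 a reduction to at most nine candidate parameters, made without sight of the outcome. Which features to merge or set aside is for the sponsor to decide.

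Under either route, state in section 7.1 that the backward selection is repeated from all candidates within each bootstrap resample, so that the optimism and shrinkage estimates include it.

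The cost is protocol and synopsis wording. Under the first route the stated error becomes less favourable; under the second, fewer features are tested in the main model. Neither needs extra patients.

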3.2 Setting

Research centres will comprise of UK specialist outpatient clinics in secondary and tertiary care as well as community specialist hubs. This setting is a feasible environment in which the reference standard (dermatologist's diagnosis, see below) can be obtained and the sample size recruited within the time and resources available. We anticipate that 50-60% of new patients referred to the vulval clinic will have LS.

There is potential for including international centres in this study, although it is anticipated that the majority will be in the UK.

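### 370 complete pairs narrowly miss the stated 0.05 margin (385 are needed at 95%), 407 does not hold 370 against a 10% loss, and the reduction rule in 7.1 leads back to about 370

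*Protocol*

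**What the plan says.** Section 7.2 of the protocol bases the calculation on a published approach, "using the recommended margin of error of ≤ 0.05", for a binary outcome present in half of clinic attenders. It continues: "A sample size of 370 people (185 people with the outcome LS and 185 non-LS) is needed to target a confidence interval of 0.45-0.55". That interval is centred on an assumed proportion of one half. The same 370 is also said to serve a second purpose, "to target a mean absolute error of 0.062 between observed and true outcome probabilities", and the calculation allows for a model "with up to nine predictors in the final dataset". No confidence level or interval method is stated.

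On the allowance for missing data, section 7.2 says: "The final recruitment figure of 407 participants includes a 10% increase for missing data". The missing-data paragraph of section 7.1 explains that this covers a loss of up to 10%, although it expects no missing data. It then adds: "This will be monitored and if less than 10% data are missing, recruitment target will be reduced accordingly". Section 6.4 withdraws anyone who lacks either the index test or the reference standard, so each such loss comes straight off the analysed number.

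The synopsis repeats 370, the interval and 407, but not the explicit limit of 0.05. Section 3.2 gives a wider expectation for the outcome: "We anticipate that 50-60% of new patients referred to the vulval clinic will have LS".

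**The concern.** Three statements about the sample size do not fit together. The margin is fixed as an upper limit, yet the number said to be needed does not reach it. The allowance for loss was made by multiplying by 1.10 rather than dividing by 0.90, so it falls short at the very loss it is meant to cover. The reduction rule then gives up the surplus over 370 when few data are missing, which is the situation the protocol expects.

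At stake is whether the study meets the precision criterion it sets for itself. The first two points concern the accuracy of what is written. The third is an operating instruction: followed as written, it would end recruitment below the number that the stated margin requires, when the recruitment already planned could have met it.

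**Working it through.** **Inputs.** Margin d at most 0.05, proportion p = 0.5, n = 370, 10% increase and 407 recruited (section 7.2); loss of up to 10% and the reduction rule (section 7.1); prevalence of 50–60% (section 3.2). The 95% level (z = 1.96) is an assumption.

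**1. The plan's own figures.** 370 × 1.10 = 407, so the recruitment figure reproduces exactly as a multiplication. The 370 does not reproduce from the margin:

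- n = z² p(1 − p)/d² = (1.96/0.05)² × 0.25 = 384.2, so 385.
- The difference is 385 − 370 = 15 pairs.

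**2. Margin at each number of complete pairs.** Half-width = 1.96 × √(0.25/n):

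| Complete pairs | Half-width | Meets 0.05? |
|---|---|---|
| 366 | 0.0512 | no |
| 370 | 0.0509 | no |
| 385 | 0.0499 | yes |
| 407 | 0.0486 | yes |

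At 370 the interval is 0.449 to 0.551.

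**3. Does another convention explain 370?** At p = 0.5 and 95%, the Wilson interval needs 381 (half-width 0.0507 at 370), the continuity-corrected normal interval needs 404, and the Clopper-Pearson half-width at 370 is 0.0521. A 90% level would need only 271. None of these yields 370. With the simple formula, p = 0.55 needs 381 and p = 0.60 needs 369.

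**4. The allowance for loss.**

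- 407 × 0.90 = 366.3, so 366 pairs remain after a full 10% loss, which is below 370.
- 1 − 370/407 = 0.091, so 407 protects 370 up to a loss of 9.1%.
- 370/0.90 = 411.1, so 412 would be needed to keep 370.

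**5. The reduction rule.** Take a loss of 5% as an illustration.

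- Reduced target by the plan's multiplication: 370 × 1.05 = 388.5, leaving 388.5 × 0.95 = 369.1 pairs. Dividing instead, 370/0.95 leaves 370.
- Fixed target: 407 × 0.95 = 386.7, so 386 pairs, which is above 385.

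With no loss, the reduced target is 370 itself. In general a fixed 407 leaves at least 385 pairs while the loss is at most 407 − 385 = 22, and 22/407 = 5.4%.

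**The case against.** The strongest reply is that the miss is trivial. At the two decimals printed, the interval for 370 is still 0.45 to 0.55, so only the upper limit of 0.05 is broken, and by 0.0009. The primary objective is to find the best predictors and build a diagnostic tool, not to estimate clinic prevalence, and no modelling step in section 7.1 turns on this difference. The figure of 385 depends on an unstated level and on the simple interval. At a prevalence of 0.60, the top of the range in section 3.2, 369 pairs are enough. All of this stands and limits the weight of the point. It does not remove it: section 7.2 itself fixes 0.5, and no 95% method tried there meets 0.05 with 370.

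On the allowance, 407 is literally 10% more than 370, and the shortfall appears only for a loss between 9.1% and 10%, at most 4 pairs. That too stands as a statement of size.

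On the reduction rule, releasing an unused allowance is coherent if 370 is the target, and section 7.1 names no floor. That the rule returns the study to about 370 is the natural reading, but an inferred one.

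A reader might infer that the model-error target of 0.062 is missed as well. The protocol gives that target without a formula, so this cannot be shown from the document and is not claimed. The 370 may indeed come from that target, but that would not make the statement about the interval correct.

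**Conclusion.** The point holds and is minor in size. Assuming a 95% interval and the protocol's own proportion of 0.5, the stated margin needs 15 more complete pairs than the 370 given. The allowance for loss is five people short of what would keep 370 at a 10% loss. The reduction rule is the part with practical effect, because it gives up a surplus that would bring the study within its margin at the low loss it expects.

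Two stronger readings are not supported. One is that the study is materially undersized: the margin goes from 0.050 to about 0.051, on a quantity that is not the primary aim. The other is that keeping 407 secures the margin: it does so only if the loss is at most 5.4%. At a full 10% loss 366 pairs remain, and keeping 385 would take 385/0.90 = 427.8, so 428, more than is planned.

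**What to change.** - **Section 7.1:** delete the sentence that reduces the recruitment target, or allow a reduction only once 385 complete pairs are in, within the planned 407.
- **Section 7.2 and synopsis:** state the confidence level, and state that a margin of at most 0.05 at a proportion of 0.5 needs 385 complete pairs. Give the margin as about 0.051 both at 370 and at 366, the number left from 407 after a full 10% loss. Say that 407 meets 0.05 only if the loss is at most 5.4%, and that it protects 370 only up to 9.1%, with 412 needed at 10%.

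This is a change of wording and adds no participants beyond the 407 already planned. The downside is that the option to stop recruiting early is lost, or limited to the time after 385 complete pairs have been reached.

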8 ADVERSE EVENTS

The occurrence of an adverse event as a result of participation within this study is not expected and no adverse event data will be collected. Patients will have their vulval condition diagnosed in line with usual clinical practice. They will be treated by their managing clinician based on the clinician diagnosis (reference standard), not based upon the Delphi-agreed diagnostic criteria (index test). If the clinician diagnosis is amended at a later stage, this will be recorded in the SHELLS database and their management will be amended according to usual practice.

8 ETHICAL AND REGULATORY ASPECTS

8.1 Ethics committee and regulatory approvals

The study will not be initiated before the protocol, consent forms and PIS have received approval / favourable opinion from the Research Ethics Committee (REC), the respective National Health Service (NHS) or other healthcare provider's Research & Development (R&D) department, and the Health Research Authority (HRA) if required. Should a protocol amendment be made that requires REC approval, the changes in the protocol will not be instituted until the amendment and revised informed consent forms and participant and GP information sheets (if appropriate) have been reviewed and received approval / favourable opinion from the REC and R&D departments. A protocol amendment intended to eliminate an apparent immediate hazard to participants may be implemented immediately providing that the REC are notified as soon as possible and an approval is requested. Minor protocol amendments only for logistical or administrative changes may be implemented immediately; and the REC will be informed.

The study will be conducted in accordance with the ethical principles that have their origin in the Declaration of Helsinki, 1996; the principles of Good Clinical Practice and the UK Department of Health Policy Framework for Health and Social Care, 2017.

